Six randomized patients with a recent diagnosis of childhood cancer who start chemotherapy will be selected, data from the clinical record will be obtained to determine if it meets the inclusion criteria. The patient identified as eligible will be visited at his place of hospitalization or in the outpatient office of the Oncology Service.

The intervention will be assigned under the balanced block scheme. Children will be randomly assigned to each of the two treatment groups using sealed envelopes.

The sequence of procedures and the complete description of the instruments can be found in the Annex "Pilot test applicator manual".

[figure not shown]
Information collection method

A data record sheet will be filled out that includes the patient's identification form (name, age, sex), type of ALL, chemotherapy phase and blood count; which will be obtained from the clinical file. It will also include the table for the determination of the WHO OM scale, the oral hygiene index and the opportunistic infection registry.

Registration and processing method.

[figure not shown]
The data will be recorded in an Epidata database and analyzed using the STATA 14 statistical program.

FLOWCHART 1

In the previous study by Rambod et al. (12), a difference in the incidence of OM of 28% was obtained and from this, for the present study the estimated sample size was 106 subjects.

Complying with one of the principles that govern clinical trials, which is to reduce the risk of the operated subjects to the minimum possible, in case of observing adverse reactions the suspension of the study will be indicated; while if there are no complications, recruitment will continue until a sample size of 53 subjects is met and at this point the intermediate analysis will be performed as shown in Flowchart 2.

ETHICAL CONSIDERATIONS

In accordance with the principles and guidelines established by good clinical practices (BPC), in accordance with the principles set forth in the Helsinki Declaration of 1964 and with the support provided in the General Health Law, in the Regulations of the General Health Law in the area of provision of Health Care Services, which establishes that the individual welfare of the subjects must sometimes prevail in a study, over the interests of science and the community.

This study will be carried out with the strict observation of the recognized scientific principles and respect, handling the affected data anonymously and confidentially.

Consent

To parents or to those who exercise parental rights of patients, we provide the information related to the study, both verbally and in writing. The master's student made an initial invitation to the parents or guardians of the minor for their child to participate in the study and read the "Informed Consent Letter" to state the purpose of the investigation and make a description of the same. In the case of patients older than 12 years, also read the "Informed Assent Letter". The signature of the parents and the minor is requested freely and voluntarily with the "Declaration of Consent / Informed Consent" after the purpose of the investigation has been understood and doubts have been clarified.

Confidentiality

To verify the confidentiality and privacy of the participants, the data will be stored in databases to which only the researchers of the study have access.

Risk

The study is classified with greater than minimum risk. The administration of zinc in doses of 50-100 mg / day is considered safe, since no adverse effects have been described at that dose.

Benefits

Patients participating in the study will have greater clinical control for the prevention of oropharyngeal mucositis, since they will be collected before the start of chemotherapy and notifications will be received to receive care from the Stomatology service in the case of treatment.

Although no difference is found in favor of the intervention and the necessary sea, the suspension of the study, measures will be taken to ensure that participants of both groups receive benefits by receiving educational oral care talks, identification of signs of OM, as well as Oral hygiene attachments and medications for the treatment of OM.

BIOSECURITY CONSIDERATIONS

In accordance with current regulations, the following is held:

- NOM-052-SEMARNAT-2005

It establishes the characteristics of hazardous waste, also mentions that expired and leftover drugs are considered hazardous waste and therefore, must finally be disposed of responsibly.⁴¹

- General law for the prevention and integral management of waste.

Article 31. The following hazardous wastes and products used, expired, withdrawn from trade or disposed of and which are classified as such in the corresponding official Mexican standard shall be subject to a management plan:

VIII. In accordance with the above, the remaining or expired doses of the drug (zinc sulfate) should be handled as hazardous waste and its disposal will be as follows:

Leftover zinc tablets will be kept in closed plastic containers and considering that the amount will not exceed 20 bottles (100 tablets per bottle) may be deposited in the SINGREM safe containers (National System for the Management of Packaging and Drug Residues AC.), which are responsible for the final disposition of expired medicines and their leftovers from homes and are located in pharmacies registered in different parts of the city.

LIMITATIONS

Because the population considered for the present study comes from two national reference centers, it is frequent that they find the cases with major complications (greater risk in terms of the presentation characteristics of LAL or late diagnosis) so they would not necessarily represent to all children of LAL in Mexico.

FINANCING

Materials: Registration formats, intraoral mirror for review, computer equipment, printer.

Economic: Laboratory tests (blood count, KOH, PCR, bacterial cultures) will be performed at the National Institute of Pediatrics and the Children's Hospital of Mexico.

The zinc sulfate drug and placebo as well as oral hygiene products and medications for the treatment of mucositis will be obtained through the Field Work Funds of the Master's and Doctorate Program in Medical, Dental and Health Sciences, will not be sponsored by pharmaceutical companies.

Humans: Master's student, master's tutor and social service assistant of Oncology.

REFERENCES

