Methods: Double-blind randomized clinical trial conducted in pediatric patients with newly diagnosed or relapsed acute lymphoblastic leukemia. The subjects will be randomized to designate them in the control group (Group1 placebo) or intervention group (Group 2 zinc). The zinc/placebo intervention will be administered orally in tablets of 50-100 mg/day, from day 1 of chemotherapy until the end of the consolidation phase (2 to 2.5 months). For the detection of OM will be used the mucositis scale of the World Health Organization and the observation times will correspond to day 1, 4, 7, 14 and 21 of each chemotherapy cycle. Patients in both groups with OM will receive the same treatment (mouthwash with Gelclair®) and will be observed daily until healing to determine the days of recovery.

Statistical analysis: Independent t-test and Chi-square test for the difference between the two study groups, ANOVA to compare the groups with respect to the severity of OM.

BACKGROUND

The leukemias are a heterogeneous group of neoproliferative processes that are characterized by a clonal expansion of transforming hematopoietic precursors cells, this infiltrate a bone marrow and invade a peripheral blood and other organs.¹ The leukemias has been classified principally by their duration in: acute or chronic and by their cell type are affected in: myeloid, lymphoid and monocytic.² The acute leukemias (AL) are the more frequent type of neoplasia in the childhood and are approximated 33% of malignance pediatric illness.¹

Acute lymphoblastic leukemia (ALL) represents 75% of all cases, being more frequent between 2 and 5 years of age.¹ The worldwide incidence of all types of ranges from 2.0 to 3.5 cases per 100,000 inhabitants per year, while in Mexico 6/100 000 inhabitants are estimated per year;³ so that Mexico is considered to be one of the countries with a high incidence and mortality rate in LA.⁴ The ratio of Lymphoid/myeloid leukemia is 6:1.⁵ In a study on the frequency of acute childhood leukemia in Mexico City, it was found that the National Institute of Pediatrics presented 27.6% of all cases, followed by the Pediatrics Hospital of Mexico "Federico Gomez" with 20.2%.⁶

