The treatment is based on polychemotherapy, which is the combination of antineoplastic drugs that seek to control cell growth and replication as well as destroy neoplastic cells in different phases of the cell cycle. In general, chemotherapy in patients with LLA consists of three phases: Induction, consolidation and maintenance, during which the prophylaxis of the central nervous system is incorporated, with intrathecal chemotherapy or high doses of chemotherapy.⁷

Induction aims to eradicate more than 99% of leukemic cells, restore normal hematopoiesis and the patient's physical condition. This phase of treatment includes the administration of glucocorticoids, with dexamethasone being the most used because it has better penetration to the central nervous system, associated with vincristine, L-asparaginase and an anthracyclinc. With induction, usually more than 90% of patients achieve complete remission. The consolidation phase improves the remission achieved by induction; Commonly the regimens include high doses of methotrexate associated with 6-mercaptopurine. The maintenance phase aims to maintain the remission already achieved. Most regimens include the combination of weekly methotrexate with daily 6-mercaptopurine. The total duration of treatment should be from 2 years to 2 years and six months.⁸

Chemotherapeutic protocols are the result of the collaboration of different study groups, in 2015 Pui et al.,⁹ conducted a review of the literature to analyze the impact of collaborative studies on advances in biology and treatment of LAL in children and adolescents, finding a 5-year overall survival rate of 82 to 93.5%. However, the substantial proportion of survivors face long-term complications; Therefore, the development of new protocols is currently aimed at optimizing the use of existing antileukemic agents, by evaluating the pharmacogenetics of normal host cells to avoid insufficient or excessive treatment.¹⁰

Oral complications secondary to chemotherapy

The lack of selectivity of antineoplastic drugs produces toxic effects in normal cells, especially in those with high replication rate, such as the cells of the basal layer of the epithelia, in which their renewal capacity is altered resulting in various complications. That is why in patients with hematologic malignancies such as LLA, oral lesions may occur secondary to direct damage of the lining epithelium by chemotherapy.⁶

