Chemotherapeutic agents are not equally stomatotoxic.¹⁵ The extent of damage depends on the drug used, the duration of treatment, the dose and the route of administration; Therefore, bolus infusion, prolonged or repeated administration, compared with low doses of chemotherapy are associated with an increased risk of developing OM. Drugs that affect DNA synthesis, such as antimetabolites (methotrexate, 5-fluorouracil) and purine analogues (cytarabine), have been shown to cause OM from 40-60%. Etoposide, cyclophosphamide, doxorubicin, daunorubicin, docetaxel and paclitaxel have also been related.¹³

In the ulcerative phase of OM there are complications such as pain, difficulty eating, swallowing and speaking, which may require the use of analgesics and nutritional support.¹² The most severe grades are related to complications such as: deterioration in quality of life, increase in the duration and cost of hospital stay, decrease in the survival rate of patients due to delayed treatment or reduction in the dose of chemotherapy, as well as a higher incidence of secondary infections and may even lead to sepsis and death.¹⁶

Dental care in pediatric patients with cancer is essential, preventive measures and specific intervention actions are required to improve oral conditions that favor good nutrition and reduce the risk of infections.¹⁶

Recent research has found that OM is the result of a complex process that begins in the submucosal endothelium and fibroblasts, with the influence of local cytokines and not just direct epithelial cell damage. Thus, through a better understanding of the common intracellular pathway of the endothelium, cell apoptosis and interactions between apoptotic and inflammatory pathways, new treatments have been developed, which although some have been used in the pediatric population, none have been accepted as the treatment of choice.¹⁴

There are various treatments for OM including medications such as amifostine, palifermin, benzydamine, HCl and pentoxifylline, low intensity laser therapy and various organic products such as zinc; however, the effects of these interventions have not been fully confirmed.¹²

Zinc

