Cancer patients will experience pain, limitation and psychological involvement due to oral OM; this debilitating condition also significantly affects nutritional intake, oral care and quality of life, representing up to 21.9% of the reasons for hospitalization.8 OM, if not properly treated or associated with prolonged neutropenia, may end in septic shock and even the death of the patient.

The use of zinc has been studied as a low-cost alternative for OM, so the realization of this study will determine the effectiveness of the use of zinc for the prevention and reduction of complications due to OM in pediatric patients with ALL of the Institute National Pediatrics.

OBJECTIVE

To assess the impact of the use of zinc in the prevention, incidence and severity of oropharyngeal mucositis in patients with acute lymphoblastic leukemia in chemotherapy (induction and consolidation phase) of the National Institute of Pediatrics and the Children's Hospital of Mexico during the period from 2019 to 2020.

SPECIFIC OBJECTIVES

1. Determine the incidence of OM in patients with ALL assigned control group (Group 1: oral care + placebo) versus the intervention group (Group 2: oral care + zinc).
2. Identify if there are differences in OM severity between Group 1 and Group 2.
3. Identify if there are differences in the recovery time of the OM between Group 1 and Group 2.
4. Identify if there is an association between the severity of OM and severe neutropenia in both groups.

HYPOTHESIS

The use of zinc reduces the incidence and severity of OM in pediatric patients with ALL in chemotherapy compared to the control group.

MATERIAL AND METHODS

Type of study: Randomized, double blind clinical trial.

Duration of the intervention: Induction and consolidation phase of chemotherapy (2 to 2.5 months).

Inclusion Period: from August 2019 to May 2020.

Study population

Target population: patients of both sexes from 3 to 18 years of age with newly diagnosed or relapsed ALL during the period from 2019 to 2020.

Study population: patients of both sexes from 3 to 18 years of age with recently diagnosed or relapsed ALL treated by the Pediatric Oncology service of the National Institute of Pediatrics and the Children's Hospital of Mexico during the period from 2019 to 2020.

Selection criteria

Inclusion criteria: Patients aged 3 to 18 years with a recent diagnosis of ALL or relapse who accept by informed consent to participate in the study.

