Exclusion criteria. Patients with another disease or systemic condition in addition to ALL. Presence of oral infections such as candidiasis, herpetic gingivostomatitis, reactive oral lesions. Children with Down syndrome, patients allergic to zinc or mannitol.

Elimination criteria: Patients who present with hypersensitivity to zinc or placebo (mannitol), those who develop a systemic condition that modifies their treatment or prevents oral care, as well as patients requesting to leave the study.

Definition of the variables

INTERVENTION VARIABLE				
	CONCEPTUAL DEFINITION	OPERATIONAL DEFINITION	TYPE	MEASUREMENT
ZINC	Trace element found in most of the body's cells, having catalytic, structural and cellular regulation functions.	Food supplement based on zinc sulfate in doses of 50-100 mg / day for prevention and treatment of oropharyngeal mucositis .	Qualitative Nominal	1. Apply 2. No apply

DEPENDENT VARIABLES				
ORAL HYGIENE	Combination of physical and chemical measures to control the formation of bacterial plaque, which is the most important risk factor in the development and evolution of caries and periodontal disease.	Oral hygiene registered with the O'Leary index (bacterial plaque on dental surfaces identified by a developer. It is obtained from the sum of stained dental surfaces / total surfaces, multiplied by 100.	Qualitative Ordinal	1. Good 0% to 15%: 2. Regulate 16% to 49%: 3. Poor: 3.50% to 100%:
OM RECOVERY DAYS	Days in which some degree of OM is clinically observed until healing.	Number of days from the clinical diagnosis of OM (Grade ≥ 1) to recovery of the oral epithelium.	Continuous	1,2 ,3 4, 5...

INDEPENDENT VARIABLES

ORAL MUCOSITIS	Inflammatory reaction that affects the entire gastrointestinal tract from the mouth to the anus caused by chemo and / or radiotherapy.	Inflammatory reaction of the oropharyngeal mucosa to chemotherapeutic drugs, according to the WHO scale.	Qualitative Ordinal	Grade 0. Healthy Grade 1. Erythema Grade 2. Ulcers Grade 3. Extensive ulcers Grade 4. Ulcers and necrosis.
PAIN	Localized and subjective sensory perception that is the result of an excitation or stimulation of specialized sensory nerve endings.	Visual scale of facial expressions	Qualitative Ordinal	0-2 No pain 3-4 Mild 5-6 Moderate 7-8 Intense 9-10 Maximum

SOCIODEMOGRAPHICAL VARIABLES

	CONCEPTUAL DEFINITION	OPERATIONAL DEFINITION	TYPE	MEASUREMENT

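### Randomised children can be eliminated for later events, and the supplied text does not say whether their mucositis grades are kept, whether assessment continues, or which children are analysed

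*Combined protocol and SAP*

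**What the plan says.** The Selection criteria list elimination separately from exclusion. Eliminated are children with hypersensitivity to zinc or to the mannitol placebo, "those who develop a systemic condition that modifies their treatment or prevents oral care, as well as patients requesting to leave the study". Under Stages of the study and data collection, the group is assigned before tablets start on day 1 of chemotherapy, so these events can fall after randomisation.

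Follow-up is long enough for that to matter. The intervention spans "Induction and consolidation phase of chemotherapy (2 to 2.5 months"), with OM graded on five days of every cycle. According to the Summary, children with OM are then "observed daily until healing to determine the days of recovery".

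The Statistical Analysis Plan is one paragraph. It names descriptive statistics, the independent t-test, the chi-square test, and an ANOVA across five time periods. It gives no analysis population, no rule for data recorded before elimination, and no rule for missing visits. The only allowance is in the Sample size calculation, where 15% for losses raises 46 to 53 per group.

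**The concern.** Randomisation makes the arms comparable at assignment. Removing children for what happens afterwards can undo that, and extra recruitment does not restore it.

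The protocol's own background gives reasons why removal could be related to the outcome. In the Oral Mucositis section, severe grades are linked to "delayed treatment or reduction in the dose of chemotherapy, as well as a higher incidence of secondary infections and may even lead to sepsis". The Justification says that "this debilitating condition also significantly affects nutritional intake, oral care and quality of life" and that "OM, if not properly treated or associated with prolonged neutropenia, may end in septic shock and even the death of the patient". The elimination wording refers to changed treatment and to prevented oral care, so an overlap is possible, though OM is not a stated trigger. The hypersensitivity trigger concerns the assigned product itself, so it could also act differently in the two arms.

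Incidence is affected as well as severity. The Background says of consolidation: "Commonly the regimens include high doses of methotrexate associated with 6-mercaptopurine". It also says that "antimetabolites (methotrexate, 5-fluorouracil) and purine analogues (cytarabine), have been shown to cause OM from 40-60" per cent. A child eliminated during induction without OM has therefore not been observed through a later period of risk. A child who leaves before healing has no complete value for recovery days.

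**Working it through.** **The plan's own figure.** The substituted expression in the Sample size calculation is [1.96·√(2·0.75·0.25) + 0.84·√(0.75·0.25 + 2·0.47·0.53)]² / 0.28² = 45.8, hence 46. Then 46 × 1.15 = 52.9, hence 53 per group. This reproduces. The step adds children; it says nothing about the data of those lost.

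**Inputs from the documents.** 53 per arm; expected OM incidence 75% (placebo) and 47% (zinc); 15% losses.

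**Assumptions.** L children per arm are lost, and all their grades are discarded. The full allowance is 0.15 × 53 = 7.95, about 8 (or 53 − 46 = 7 by the plan's own arithmetic). Observed counts are set close to 75% and 47% of those who remain. P-values are from the uncorrected chi-square test.

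**Bounds among all 53 per arm.** With a and b the observed placebo and zinc events:
- lowest difference = (a − b − L)/53 (no lost placebo child had OM, every lost zinc child did)
- highest difference = (a + L − b)/53 (the reverse)

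| L per arm | Observed | Difference | Lowest | Highest |
|---|---|---|---|---|
| 8 | 34/45 v 21/45 | 28.9 points, p=0.005 | (34−29)/53 = 9.4 points, p=0.32 | (42−21)/53 = 39.6 points |
| 7 | 34/46 v 22/46 | 26.1 points, p=0.010 | (34−29)/53 = 9.4 points, p=0.32 | (41−22)/53 = 35.8 points |
| 4 | 37/49 v 23/49 | 28.6 points | (37−27)/53 = 18.9 points, p=0.047 | (41−23)/53 = 34.0 points |
| 2 | 38/51 v 24/51 | 27.5 points | (38−26)/53 = 22.6 points, p=0.017 | (40−24)/53 = 30.2 points |

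**Moderate cases at L = 8.**
- 6 of the 8 lost placebo children and 4 of the 8 lost zinc children had OM: 40/53 v 25/53, 28.3 points, p=0.003.
- 6 of 8 placebo and all 8 zinc: 40/53 v 29/53, 20.8 points, p=0.025.

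**Effect of keeping recorded grades at L = 8.** Suppose OM had already been recorded before elimination in 6 placebo and 4 zinc children, and those grades are kept. Only 2 placebo and 4 zinc outcomes are then unknown.
- Lowest: 40/53 v 29/53 = 11/53 = 20.8 points, p=0.025.
- Highest: 42/53 v 25/53 = 17/53 = 32.1 points.

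The width falls from 16/53 = 30.2 points to 6/53 = 11.3 points. In this example, most of the uncertainty comes from discarding data already in hand.

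**The case against.** The strongest reply is that the rule is narrower than it looks. The exclusion criteria bar another disease or systemic condition besides leukaemia, so a systemic condition that develops later may simply mean a new comorbidity. Under OM treatment, tablets, oral care and observation continue when OM occurs. Neutropenia and opportunistic infections are recorded as variables, which suggests that they are expected events. Patient and investigator are blinded, which limits knowing differences in who is removed. The Background puts OM onset 3 to 10 days after chemotherapy starts, so many cases would be recorded before a child leaves.

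Most of this stands, and it rules out several stronger readings:
- A reader might infer that the plan removes the worst OM cases. The documents make OM neither an elimination criterion nor a reason to stop observation.
- A reader might infer from 9.4 points and p=0.32 that the incidence result would probably be lost. That is an extreme corner, and the moderate cases above remain significant.
- A reader might infer that all endpoints are equally exposed, because the bounds have the same width for any binary outcome with the same L. That follows only from giving each the same L. Incidence is settled at the first grade of 1 or more, whereas the highest grade can still rise and recovery needs healing to be seen.
- A reader might extend the loss of randomised comparison to every objective. Recovery among children with OM and the association of severity with neutropenia are not randomised comparisons in the first place.
- A reader might conclude that no rule exists anywhere, or that a completers-only analysis is planned. The flowcharts and manuals were not supplied, and the text is silent rather than committed to dropping anyone.

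None of this supplies the missing rule. Blinding does not restore the randomised groups if children are dropped for later events, and the plan itself expects losses.

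**Conclusion.** The point holds for incidence and severity: a stated rule eliminates children after assignment, and the supplied text does not keep their data, continue their assessment or define who is analysed. This should be fixed, with moderate confidence. With all grades discarded for an assumed 8 children per arm, an observed 28.9 points is compatible with 9.4 to 39.6 points. With 2 per arm, an observed 27.5 points is compatible with 22.6 to 30.2. The loss counts, the observed counts and the outcomes of lost children are assumptions. The documents support no estimate of how many children would be eliminated or of the direction of bias, and a rule in the unsupplied flowcharts or manuals cannot be excluded.

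**What to change.** In the protocol and SAP, before the intermediate analysis at 53 subjects and before the A/B codes are revealed:

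1. Make elimination a reason to leave study tablets, not the analysis. Decisions about tablets stay with the investigators.
2. Continue the scheduled OM assessments, and observation to healing, after elimination unless consent is withdrawn.
3. Analyse incidence and severity in all randomised children by assigned group, using every recorded grade.
4. State in advance how a child who leaves without recorded OM is counted, and how missing visits are handled in the five-time comparison.
5. Give best- and worst-case bounds, and the analysis without eliminated children, as sensitivity analyses only.
6. Treat recovery days as time to healing, censored at the last assessment, and describe children with OM as a non-randomised subset.
7. Report eliminations by arm and reason.

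The cost is wording and a few extra assessments, some of them in outpatients. The effect will be somewhat diluted by children who are off tablets. Censoring may still be informative if a child leaves because OM is worsening, so continued observation matters more than the censoring rule.

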AGE	Life time elapsed from birth to the current date.	Life time in years recorded in the clinical record.	Quantitative Discreet	Years 0 a 18
SEX	Physiological and sexual characteristics with which men and women are born.	Biological characteristics recorded in the clinical file as female and male.	Qualitative Nominal Dichotomous	1. Female 2. Male

CONFUSORY VARIABLES				
ACUTE LEUKEMIA LYMPHOBLASTICS (LAL)	Neoplastic disease that results from a clonal proliferation of lymphoid precursors (lymphoblasts), which infiltrates bone marrow, produces a variable degree of pancytopenia and can compromise different organs and / or systems.	Type of leukemia recorded in the clinical file according to the immunophenotype.	Qualitative Nominal	1. Pro B leukemia 2. Common leukemia 3. Pre-B leukemia 4. Mature leukemia B 5. T leukemia (precursors) 6. T leukemia (mature)
NEUTROPENIA	Reduction of peripheral blood neutrophil count .	Absolute neutrophil count obtained by laboratory test (blood count).	Qualitative Ordinal	0. Absence of neutropenia 1. Mild: 1,000-1,500 / ml 2. Moderate: 500-1,000 / ml 3. Severe: <500 / ml
OPPORTUNIST INFECTIONS	Infections in immunosuppressed patients, whether of bacterial, fungal or viral origin.	Record of suggestive lesions by C. albicans and determination by means of KOH, suggestive lesions of herpes and determination by PCR, suggestive bacterial lesions and detection through cultures.	Qualitative Nominal	0. Absent 1. Fungal 2. Bacterial 3. Viral

STUDY DESIGN

Double blind clinical trial

Sampling: Sequential non-probabilistic until the required number of participants is completed.

Randomization: sealed envelopes for group assignment.

Sample size calculation

Formula for the difference of proportions (incidence of OM).

$$\frac{[Z_{\alpha} \sqrt{2\pi_1(1-\pi_1)} - Z_{\beta} \sqrt{2\pi_1(1-\pi_1) + 2\pi_2(1-\pi_2)}]^2}{(\pi_1 - \pi_2)^2}$$

Assumptions:

$$\alpha = 0.05$$

$$\text{Power} = 0.90$$

Rambod study findings: The effect of zinc sulfate on prevention, incidence, and severity of OM in leukemia patients undergoing chemotherapy.

$$Z_{\alpha} = 1.96$$

$$Z_{\beta} = -0.84$$

$$n = 86$$

$$\pi_1 = 75\%$$

$$\pi_2 = 47\%$$

$$\pi_1 - \pi_2 = 28\%$$

$$\frac{[1.96 \sqrt{2(0.75)(0.25)} - (-0.84) \sqrt{(0.75)(0.25) + 2(0.47)(0.53)}]^2}{(0.75 - 0.47)^2} = 46$$

41/5000

15% losses = 53 patients per group

Statistical Analysis Plan

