Descriptive statistics will be used to characterize the population using measures of central tendency and dispersion for continuous variables and distributions of relative and absolute frequencies for categorical variables. Independent t-test and Chi-square test for the difference between the two study groups. Analysis of variance (ANOVA) to compare the two groups with respect to the OM in the five time periods.

METHODOLOGY

Randomization

The randomization will be taught by [name] [name], assigned to the Oncology service, who is unaware of the objective of the study.

The randomization technique will be carried out through sealed envelopes, which will indicate the bottle that will correspond to the patient, identified as treatment "A" and "B". Likewise, to ensure that the groups are balanced, blocks of 6 sealed envelopes containing 3 patients will be made for each group.

Blinding

The patient and the investigator will be blinded; for this, the 50 mg zinc and placebo tablets will be similar in size, color, shape, weight and taste; the bottles will be classified into codes A and B, which in turn will have the same shape, size and color. All of the above will be done through the Pharmaceuticals GREMAR S.A. de C.V., which is a Mexican company that has a line of food supplements located in Mexico City.

An independent investigator (who will be blinded for the purpose of the study) will be requested to receive the medications (zinc / placebo) prepared by the Pharmaceuticals GREMAR S.A. of C.V., so that it provides to the principal investigator only the bottles coded as "A" and "B". At the end of the intervention, the independent investigator will be asked to reveal the coding of the medications to determine which group (Group 1 placebo or Group 2 zinc) corresponds to treatment A and B respectively.

Instruments

WHO OM scale

The oral mucositis scale proposed by the World Health Organization (WHO) in 1979 will be used. This instrument was designed based on objective signs (erythema or ulcer) and subjective signs (mucosal sensitivity, ability to swallow).

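### The sample size is labelled 90% power but computed with the 80% quantile; 53 per group with 15% losses gives about 79%

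*Combined protocol and SAP*

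**What the plan says.** The sample size calculation under Study Design sizes the trial on the difference between two proportions, the incidence of oral mucositis. Its assumptions are α = 0.05, power = 0.90, Zα = 1.96, Zβ = -0.84, and incidences of 75% and 47% taken from a published trial of zinc sulfate in adults with leukaemia. The substituted expression uses 0.84 and yields 46. Dropout is then added: "15% losses = 53 patients per group". The text after Flowchart 1 repeats the total: "for the present study the estimated sample size was 106 subjects". Allocation is 1:1, by "blocks of 6 sealed envelopes containing 3 patients will be made for each group". The Statistical Analysis Plan names the comparison as "Independent t-test and Chi-square test for the difference between the two study groups". Nowhere does the document mention 80% power or explain the value of Zβ.

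**The concern.** The stated power and the stated Zβ cannot both be right. A Zβ of -0.84 corresponds to 80% power and -1.28 to 90%. The value 0.84 appears twice, in the list of assumptions and in the substituted expression, and it drives the result, so it is not a stray character.

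Incidence is the first specific objective, leads the hypothesis, and is the only endpoint sized. Anyone reading a null result, or judging whether a placebo-controlled study in children that the protocol itself classes as above minimal risk is adequately sized, would rely on a 10% chance of missing the assumed effect. If the true chance is about twice that, a negative result is weaker evidence against zinc than the plan implies.

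**Working it through.** **Inputs** (all from the sample size calculation unless noted): π1 = 0.75, π2 = 0.47, difference 0.28; Zα = 1.96, which is two-sided 0.05 (sidedness is not stated in words); Zβ = -0.84; stated power 0.90; losses 15%; 1:1 allocation (Randomization section); chi-square test (Statistical Analysis Plan).

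**Step 1. Reproduce the plan's figure.** The substituted expression is

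[1.96·√(2·0.75·0.25) + 0.84·√(0.75·0.25 + 2·0.47·0.53)]² / 0.28²
= [1.96·0.6124 + 0.84·0.8281]² / 0.0784
= [1.2002 + 0.6956]² / 0.0784 = 45.84, rounded to 46.

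Then 46 × 1.15 = 52.9, rounded to 53, and 2 × 53 = 106. The plan's numbers are reproduced.

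**Step 2. Change only Zβ to the 90% value.** With 1.2816 the same expression is [1.2002 + 1.0613]² / 0.0784 = 65.2. So 46 is the result for the 80% quantile, not the 90% quantile.

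**Step 3. Compare with the formula as printed.** The symbolic formula has a factor of 2 on both terms under the second root; the substituted line has it on only one. As printed, with 0.84, it is [1.2002 + 0.84·0.9345]² / 0.0784 = 50.3. A reader cannot get 46 from the stated formula.

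**Step 4. Use the standard pooled formula.** With mean incidence (0.75 + 0.47)/2 = 0.61:

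n = [1.96·√(2·0.61·0.39) + Zβ·√(0.75·0.25 + 0.47·0.53)]² / 0.28²
= [1.96·0.6898 + Zβ·0.6608]² / 0.0784.

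- 80% power: 46.4 per group (47 if rounded up).
- 90% power: 61.7 per group, so 62.

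**Step 5. Evaluable patients.** 53 × 0.85 = 45.05, so about 45 per group. Inflating by 1.15 rather than dividing by 0.85 falls slightly short: 46/0.85 = 54.1, so 55 would be needed to retain 46.

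**Step 6. Power actually delivered.** Inverting the pooled formula, power = Φ{(0.28·√n − 1.96·0.6898) / 0.6608}. At n = 45 the argument is 0.797, giving 0.787. The exact figures come from summing binomial probabilities over the rejection region of the uncorrected chi-square test.

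| Evaluable per group | Pooled normal | Exact, uncorrected chi-square |
|---|---|---|
| 45 (53 less 15%) | 78.7% | 78.9% |
| 46 | 79.6% | 79.0% |
| 53 (no losses) | 85.1% | 85.8% |

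With a Yates correction, exact power at 45 per group falls to about 71%.

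**Step 7. Does the choice of formula matter?** For two-sided 0.05 and 90% power, the required evaluable number per group is 59 (unpooled), 62 (pooled), 64 (twice the variance at the mean proportion) or 69 (continuity-corrected). None is near 46, and all exceed 53.

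**The case against.** There are four points on the other side.

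- **One-sided reading.** The hypothesis is directional and sidedness is not written out. At one-sided 0.05, 53 per group without losses would give 91.4%. But the plan prints 1.96, and after losses the one-sided figure is 87.0%. The statement that the size does not reach 90% should therefore carry its two-sided condition, but this reading does not rescue the plan.
- **A variant that lands near 53.** Dropping both factors of 2 under the second root and using 1.28 gives 53.5. This is a coincidence: the plan prints neither that formula nor that Zβ, and it reaches 53 as 46 plus losses.
- **Which value is the slip?** The document does not show whether 0.90 or -0.84 was intended. This is a fair point. It affects the choice of remedy, not the finding.
- **Rounding.** The pooled formula gives 46.4, strictly 47 when rounded up, so 46 sits just under 80%. This is also fair, and is the reason to report the delivered power beside the nominal one.

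The missing factor of 2 and the dropout inflation are minor. The former could be a typing slip, and the latter changes power by less than one percentage point.

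**Conclusion.** The concern holds. The calculation was done at 80% power and labelled 90%. Under the plan's own assumptions, power is about 79% with 45 to 46 evaluable patients per group, and 85% if nobody is lost. The type II error is about 21% rather than 10%.

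This rests on true incidences of 75% and 47%, two-sided 0.05, an uncorrected chi-square test, 15% losses in each group, and no allowance for the interim analysis planned at 53 subjects. Changing the two-sided sample size formula does not alter the conclusion.

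**What to change.** In the sample size calculation, replace the power of 0.90 with a nominal 0.80, which matches Zβ = -0.84. State beside it that 53 randomised per group leaves about 45 evaluable after 15% losses, with delivered power of about 79% (two-sided 0.05, 75% versus 47%). Replace the printed formula with the pooled two-proportion formula, show that it gives 46.4 at 80% power, and make the symbolic and substituted lines agree. Keep 106 patients. The cost is wording and a less favourable power figure; enrolment, budget and procedures do not change.

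If the sponsor did intend 90%, the size must rise instead: 62 evaluable per group, 62/0.85 = 72.9, so 73 randomised per group and 146 in total, 40 more than planned. The total after Flowchart 1 would then change too.
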